7.1.7 Supplying/Order, Storage, and Handling

Supplied: Photofrin® (porfimer sodium) for Injection is supplied as a freeze-dried cake or powder as follows: NDC 76128-155-75, 75 mg vial

Supplier: Pinnacle Biologics, Inc., as subsidiary of Concordia Laboratories Inc.

Agent Ordering: The study site's investigational pharmacy will place orders with Pinnacle Biologics using their trial specific order form.

Storage: Photofrin® freeze-dried cake or powder should be stored at Controlled Room Temperature 20-25 °C (68-77 °F) [

Spills and Disposal: Spills of Photofrin® should be wiped up with a damp cloth. Skin and eye contact should be avoided due to the potential for photosensitivity reactions upon exposure to light; use of rubber gloves and eye protection is recommended. All contaminated materials should be disposed of in a polyethylene bag in a manner consistent with local regulations.

Accidental Exposure: Photofrin® is neither a primary ocular irritant nor a primary dermal irritant. However, because of its potential to induce photosensitivity, Photofrin® might be an eye

and/or skin irritant in the presence of bright light. It is important to avoid contact with the eyes and skin during preparation and/or administration. As with therapeutic over dosage, any overexposed person must be protected from bright light.

7.2 Photodynamic Therapy (PDT) Lasers

The following PDT Lasers may be used to administer the prescribed light dose of 240 J cm^{-2} , with the output laser power at the fiber tip ranging from 1.0 to 4.0 watts. One or two lasers may be used at a time to administer the PDT. When utilizing two lasers any combination of the laser listed or two of the same can be used. Please notify the Sponsor Investigator and the Industry Collaborator, Pinnacle Biologics, Inc. to ensure availability and approval of the PDT Laser for each enrolled case.

- Angiodynamics DIOMED 630 PDT Laser
- Laserscope KTP/532[®] Surgical Laser System (Series 800)
- Laserscope KTP/YAG[®] Surgical Laser System (Series 800)

7.3 Photodynamic Therapy (PDT) Light Diffusers: Optical Fibers

Optical fibers serve to diffuse the laser light in the brain tumor cavity. One optical fiber will be needed for each laser. Optical fibers must be sterilized one time use only. Currently, the protocol is using a spherical light diffuser manufactured by MedLightSA, Model SD200.

8.0 EVALUATIONS/MATERIAL AND DATA TO BE ACCESSIONED

8.1 Required Clinical and Laboratory and Disease Evaluations

A list of the required clinical and laboratories has been provided in Appendix 1. This includes a table of the study specific and standard of care events and evaluations necessary to answer the primary and secondary aims as well as additional evaluations of the patient's medical records, which should be reported in the patients study record for the overall survival analysis and data safety monitoring.

8.2 Follow-up

Data from the subjects' medical records will be collected up to three years following completion of the protocol therapy. Follow-up data are expected to be submitted per the Case Report Forms (CRFs) schedule. This long-term follow-up from Week +5 to Week +156 (3-Year follow-up) will be evaluated as clinically indicated, and/or according to their Anti—cancer therapy follow-up schedule up to Year +3. During this time, the study coordinator will report data from the medical record on study specific CRFs periodically. Current follow-up data must be reported for all required and routine semiannual DSMC reviews, study progress reports, including the FDA and IRB Annual Reports.

9.0 CRITERIA FOR REMOVAL FROM PROTOCOL THERAPY AND OFF STUDY CRITERIA

9.1 Criteria for Removal from Protocol Therapy

1. Refusal of further protocol therapy by patient/legally authorized representative
2. Physician determines it is in patient's best interest.
3. Patient becomes pregnant while on study.

Patients who are off protocol therapy are to be followed until they meet the criteria for Off Study (see below). Follow-up data will be required unless consent was withdrawn.

9.2 Off Study Criteria

1. Death
2. Lost to follow-up
3. Withdrawal of consent for any further data submission
4. The third anniversary of the date the patient was enrolled on this study

10.0 STATISTICAL CONSIDERATIONS

10.1 Study Design

This Phase II study includes adults with recurrent high-grade gliomas refractory to first line treatment (concurrent radiation and Temodar followed by maintenance Temodar). Eligible patients will consist of individuals with supratentorial recurrent high-grade gliomas that are surgically amenable, are not multi-focal and are without leptomeningeal spread. Eligible patients will have injection of Photofrin® at 2.5 mg kg^{-1} , followed by surgical resection of the tumor 24 hours later. Craniotomy and tumor resection will be carried out in the standard fashion in order to achieve the maximum tumor resection compatible with preservation of neurological function. Tissue sample will be evaluated via frozen technique and discussed with the neurosurgeon before proceeding with Photofrin® activation. Patient must have dx of a high-grade glioma before the surgery to be a candidate. Activation of residual Photofrin® in the tumor bed, after resection, will be performed using an intra-operative laser with set light dose of 240 J cm^{-2} and wavelength at 630 nm. Patients will receive standard post-operative care including observation in the post-anesthesiology recovery unit followed by post-operative computerized tomography (CT) of the brain and close monitoring in the neuro-intensive care unit (NICU). Magnetic resonance imaging (MRI) of the brain will be obtained on Day +2 (± 1 day) following the surgery. An MRI will be obtained again at 4 weeks after surgery. Patient will be closely monitored at Froedtert Health-MCW for toxicities associated with Photofrin®.

This is a single arm Phase II study of Photofrin® with set dosing of 2.5 mg kg^{-1} body weight in adult patients with recurrent or refractory high-grade glioma. The primary objective of this study is to evaluate antitumor activity of Photofrin® and laser light activation by evaluating 6 month relapse-free as well as overall survival for three years post PDT treatment. We will follow progression-free survival and overall survival for three years post PDT treatment.

Any individual over the age of 18 with a recurrent/refractory high-grade glioma meeting the criteria for the study will be considered a candidate. Photofrin® will be dosed at 2.5 mg kg^{-1} .

10.2 Sample Size and Study Duration

The sample size is based on a single-arm phase II study designed to detect an increase in the 6-month relapse-free survival rate from the historical value of 35% (treated as fixed) to 55%. With 29 subjects with known 6-month outcome, the study will have 80% power to detect such an increase at a one-sided 10% significance level. This calculation is slightly conservative, because

it does not incorporate the increase in the estimated survival rate from censored observations, thus the actual power might be slightly higher. A censoring rate of less than 5% is expected, so 30 patients will be enrolled in the study. The following table shows the estimated power of the study under various hypothetical values of 6-month relapse-free survival.

6-month RFS	Power
45%	43%
50%	64%
55%	82%
60%	93%
65%	98%

10.3 Methods of Analysis

Survival probabilities will be estimated by using the product limit estimate technique. Overall survival and Relapse-free survival will be visualized using Kaplan-Meier plots. Greenwood's formula will be used to estimate the variance. The 6-month relapse free survival will be compared to the historical control value of 35% via a one-sided z-test at a 10% significance level.

10.4 Methods of Analyses for Secondary Objectives

In this single arm phase II trial, the secondary objectives are considered exploratory and will be reported descriptively based on appropriate statistical methods and accounting for patients who may undergo additional anticancer therapy post documentation of a sustained objective response. It is not possible to determine how many patients will provide data that may be used to address each of the secondary objectives. Central review histological diagnoses will be compared with diagnoses reported by the treating site. We will assess the potential impact of any differences on primary conclusions of this study. Considerations will be accounted for when making comparisons of survival and disease free survival for recurrent glioma patients. Refer to Appendix 4

10.5 Inclusion of Genders and Minorities

The study is open to all participants regardless of gender or ethnicity. Review of accrual to past studies of new agents demonstrates the accrual of both genders and all NIH-identified ethnicities

PDT Phase II Trial – Glioma Tumors In Adults

to such studies. The small number of patients entered into this trial will obviate any analysis of variation in response rate with gender or ethnicity.

11.0 EVALUATION CRITERIA

11.1 Common Terminology Criteria for Adverse Events (CTCAE)

This study will utilize version 4.0 of the CTCAE of the National Cancer Institute (NCI) for toxicity and performance reporting. A copy of the CTCAE version 4.0 can be downloaded from the CTEP website. Additionally, toxicities are to be reported on the appropriate case report forms. Refer to sections 12 and 13 for details.

Please note: 'CTCAE v4.0' is understood to represent the most current version of CTCAE v4.0 as referenced on the CTEP website (ie, v4.02 and all subsequent iterations prior to version 5.0).

11.2 Methodology to Determine Tumor Measurement

Radiographic response should be determined in comparison to the tumor measurement obtained at pretreatment baseline for determination of response, and the smallest tumor measurement at either pretreatment baseline or after initiation of therapy should be used for determination of progression. In the event that the radiographic changes are equivocal and it is unclear whether the patient is stable or has developed progressive disease, observe the patient closely, for example at 4-week intervals. If subsequent imaging studies demonstrate that progression has occurred, the date of progression should be the date of the scan at which this issue was first raised. The determination of radiographic response after treatment with agents, such as antiangiogenic therapies, that affect vascular permeability is particularly difficult. In these patients, consideration should be given to performing a second scan at 4 weeks to confirm the presence of response or stable disease. All measurable and nonmeasurable lesions should be assessed using the same techniques as at baseline. Ideally, patients should be imaged on the same MRI scanner, or at least with the same magnet strength, for the duration of the study to reduce difficulties in interpreting changes.

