3.2 Patient Screening Process and Eligibility Assessment

3.2.1 Neuro-Oncology Tumor Board Patient Assessment

Potentially eligible patients will be screened by the Neuro-oncology Tumor Board, which is a group of MCW Neurosurgeons, Neuro-oncologists, a Pathologist, and a Radiologist. This group meets on a weekly basis to review cases. The team's review of the medical history, laboratory, pathology, and imaging results for each case is part of the standard clinical practice. Indication for tumor resection will be determined by evaluating all available imaging studies. This includes variety of specialized MRIs, which are completed on a case-by-case basis with prior insurance approval. If there is not enough evidence to reasonably rule out false positive MRIs, or pseudoprogression by the Neuro-oncology Tumor Board, the patient will not meet eligibility criteria. This is because patients must be clinically indicated for gross tumor resection as part of their standard of care plan for their disease status. Refer to Section 4.

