11.3 Response Criteria

Secondary outcomes will be measured using the response assessment for Neuro-oncology (RANO) criteria⁵⁸ applied to follow-up medical imaging. Specifically, complete response, partial response, stable disease or progressive disease will be determined using volumetric measurements of brain tumor enhancement and clinical measures of neurological decline.

1. Complete response requires all of the following: complete disappearance of all enhancing measurable and nonmeasurable disease sustained for at least 4 weeks; no new lesions; stable or improved nonenhancing (T2/FLAIR) lesions; patients must be off corticosteroids (or on physiologic replacement doses only); and stable or improved clinically. Note: Patients with nonmeasurable disease only cannot have a complete response; the best response possible is stable disease.
2. Partial response requires all of the following: > 50% decrease compared with baseline in the sum of products of perpendicular diameters of all measurable enhancing lesions sustained for at least 4 weeks; no progression of nonmeasurable disease; no new lesions; stable or improved nonenhancing (T2/FLAIR) lesions on same or lower dose of corticosteroids compared with baseline scan; the corticosteroid dose at the time of the scan evaluation should be no greater than the dose at time of baseline scan; and stable or improved clinically. Note: Patients with nonmeasurable disease only cannot have a partial response; the best response possible is stable disease.
3. Stable disease will require all of the following: does not qualify for complete response, partial response, or progression; stable nonenhancing (T2/FLAIR) lesions on same or lower dose of corticosteroids compared with baseline scan. In the event that the corticosteroid dose was increased for new symptoms and signs without confirmation of disease progression on neuroimaging, and subsequent follow-up imaging shows that this increase in corticosteroids was required because of disease progression, the last scan considered to show stable disease will be the scan obtained when the corticosteroid dose was equivalent to the baseline dose.

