4. Progression will be defined by any of the following: > 25% increase in sum of the products of perpendicular diameters of enhancing lesions compared with the smallest tumor measurement obtained either at baseline (if no decrease) or best response, on stable or increasing doses of corticosteroids; significant increase in T2/FLAIR nonenhancing lesion on stable or increasing doses of corticosteroids compared with baseline scan or best response after initiation of therapy not caused by comorbid events (e.g., radiation therapy, demyelination, ischemic injury, infection, seizures, postoperative changes, or other treatment effects); any new lesion; clear clinical deterioration not attributable to other causes apart from the tumor (e.g., seizures, medication adverse effects, complications of therapy, cerebrovascular events, infection, and so on) or changes in corticosteroid dose; failure to return for evaluation as a result of death or deteriorating condition; or clear progression of nonmeasurable disease.

These criteria are published and currently accepted in the neuro-oncology community⁵⁸. The imaging interpretation will be completed by a board certified neuro-radiologist, while the neurological outcome/status will be assessed by a board certified neurologist/neuro-oncologist.

PDT Phase II Trial – Glioma Tumors In Adults

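### Response is scored against the pre-operative MRI, so resection alone can meet the size part of CR or PR

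*Combined protocol and SAP*

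**What the plan says.** Section 11.2 sets two different references. For response: "Radiographic response should be determined in comparison to the tumor measurement obtained at pretreatment baseline for determination of response". For progression: "the smallest tumor measurement at either pretreatment baseline or after initiation of therapy should be used for determination of progression".

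Section 11.3 follows the same split. PR needs a more than 50% "decrease compared with baseline in the sum of products of perpendicular diameters". Progression by size is more than a "25% increase in sum of the products of perpendicular diameters of enhancing lesions compared with the smallest tumor measurement". CR needs all enhancement to be gone. CR and PR must also last at least 4 weeks, with no new lesion, no worsening on T2/FLAIR or clinically, and a steroid condition. For CR, steroids must be stopped or at replacement dose; for PR, "the corticosteroid dose at the time of the scan evaluation should be no greater than the dose at time of baseline scan".

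The order of events is fixed elsewhere. Section 3.2.1 says "patients must be clinically indicated for gross tumor resection as part of their standard of care plan". The baseline brain MRI belongs to the pre-treatment work-up (Section 5.1.2; Appendix 1, Day -30 to Day 0). Photofrin is given on Day 0; resection, then PDT in the cavity, follow on Day +1 (Sections 5.1.3 to 5.1.5, Appendix 1). Section 5.1.7 requires brain MRI at Day +2 (±1 day), Week +4 (±3 days) and Week +24. Section 5.1.6 gives the first of these the task of judging how complete the resection was. No section gives it a role in response.

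Objective 1.2.4 reports CR, PR, stable and progressive disease against historical controls, and objective 1.2.2 looks at remission rate against historical data. The DSMC progress reports in Section 13.3.1 list response. Section 10.4 calls the secondary objectives exploratory and descriptive.

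**The concern.** A large planned reduction in tumor lies between the reference scan and every scan compared with it. CR and PR as defined therefore combine how much the surgeon removed with whatever PDT did to the remainder. Because progression is judged from the smallest measurement and response from the pre-operative one, a residual that has not shrunk at all since surgery, or has grown by up to 25%, can still count as PR by size.

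At stake is the meaning of the response rate under objectives 1.2.2 and 1.2.4 and in the DSMC reports. A reader would take it as evidence of PDT activity, and setting it beside a historical rate would compare like with like only if that rate had the same baseline.

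**Working it through.** The plan states no figure for response. Its power table for the primary endpoint reproduces: with 29 patients and success declared at 14 or more relapse-free at 6 months, the exact one-sided error at 35% is 0.098. Power at 45, 50, 55, 60 and 65% is 0.431, 0.644, 0.820, 0.929 and 0.979, against 43, 64, 82, 93 and 98% in Section 10.2. Response does not enter that calculation.

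Inputs from Section 11.3, for tumor size only. Let B be the pre-operative product of diameters and N the smallest post-operative product.

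- PR by size: current < 0.50 B.
- Progression by size: current > 1.25 N.

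1. **Surgery alone can reach PR.** A 3.0 × 3.0 cm lesion reduced to 2.1 × 2.1 cm goes from 9.00 to 4.41 cm²: 4.41/9.00 − 1 = −51%. If both diameters shrink equally, the cut lies at a diameter ratio of √0.50 = 0.707.

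2. **PR can become the same as not progressed.** A scan without size progression has current ≤ 1.25 N. If N < 0.40 B, then 1.25 N < 1.25 × 0.40 B = 0.50 B, so every such scan meets the PR size rule. A numerical check over growth of 0 to 25% agrees: it holds at N/B = 0.30, 0.39 and 0.399, and fails at 0.40, 0.41 and 0.45.

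3. **Worked example.**

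| Scan | Product (cm²) | Against pre-operative | Against Day +2 |
|---|---|---|---|
| Pre-operative | 9.0 | – | – |
| Day +2 | 3.0 | −67% | – |
| Week +24 | 3.6 | −60% | +20% |

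   The progression limit is 1.25 × 3.0 = 3.75 cm², so 3.6 is not progression. The residual has grown, yet it is PR by size.

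4. **CR.** If all enhancement is removed, the CR size rule holds until enhancement reappears.

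5. **Nothing else in Section 11.3 separates the two effects.**
   - The 4-week condition: from Day +2 (±1) to Week +4 (Day 25 to 31) is 25 − 3 = 22 to 31 − 1 = 30 days. Those two scans can satisfy it when at least 28 days apart; otherwise a later scan can. For a tumor reduced by surgery, it shows only that the residual has not regrown.
   - The note "Patients with nonmeasurable disease only cannot have a complete response; the best response possible is stable disease" does not name the scan at which measurability is judged. Read against the pretreatment baseline, it does not exclude a patient whose measurable tumor was then removed.
   - The exception for "postoperative changes, or other treatment effects" applies to T2/FLAIR progression, not to CR or PR.
   - Steroid, T2/FLAIR, new-lesion and clinical conditions can block a response, but cannot attribute one.

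6. **Which measure.** Objective 1.2.4 and the opening of Section 11.3 call the measurements volumetric, while the PR item uses products of diameters. The examples above use products. The choice matters: for a single sphere shrinking uniformly (my assumption), halving the product takes a volume reduction of 1 − 0.50^1.5 = 64.6%.

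**The case against.** The strongest case against acting is that the point concerns one component of a secondary, descriptive outcome. Section 10.4 promises no response test, Section 13.3.3 has no interim efficacy analysis, and the footnote to the stopping table in Section 13.3.4 counts SAEs only. Degree of resection is already assessed, so a report could simply show it. Nor does a post-operative reference isolate PDT: the scan is taken after PDT, whose necrotic reaction may evolve over several days (Section 7.1.2), and Section 5.2.2 allows other anticancer therapy from 1 month. One could instead call CR and PR uninterpretable after resection.

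Much of this stands. It limits the importance of the point and means the remedy is an improvement, not a cure. It does not rescue the definition: a descriptive rate should still describe what it is named for, and showing extent of resection alone would leave a grown residual labeled PR by size.

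Three stronger readings are tempting and not supported:

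- That 6-month RFS is inflated. Progression is judged from the smallest measurement, which can be a post-operative scan, so this mechanism does not reach it.
- That a good resection automatically gives CR or PR. The other conditions must also hold.
- That Appendix 4 is deficient for lacking response rates. Section 10.4 cites it in connection with survival and disease-free survival.

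**Conclusion.** The point holds for the size part of CR and PR. As written, resection alone can meet it. Once the smallest post-operative product is below 40% of the pre-operative one, or all enhancement has been removed, the size part of response says no more than that the tumor has not progressed by size.

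The consequence is confined to objectives 1.2.2 and 1.2.4 and the response items in the DSMC reports. No test, stopping rule or primary-endpoint power depends on it. The number of spurious responses cannot be computed, because the documents give no rate for extent of resection or residual disease. The 40% result needs only the plan's two thresholds; the centimeter examples also assume the product-of-diameters rule. The change should be made, but the primary analysis does not hinge on it.

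**What to change.** In Sections 11.2 and 11.3:

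- (a) Make the already required early post-operative MRI the reference for the tumor-size part of CR and PR. First reconcile its timing: Section 5.1.6 says 1 to 3 days after PDT, while Sections 5.1.7 and 10.1 say Day +2 (±1 day), in 10.1 counted from surgery. With PDT on Day +1, the lower end of that window on the study calendar is the day of surgery. Also reconcile Appendix 1, which as extracted marks a required MRI at Week 3 as well as Week 4, with Section 5.1.7, which lists only Week +4.
- (b) Report CR and PR only in patients with measurable residual enhancement on that scan. Report the others as not evaluable for response, by progression status.
- (c) Report extent of resection, and the start of any other anticancer therapy, alongside each response, including in DSMC reports.
- (d) State that every progression reference, including the T2/FLAIR one, stays as it is, so that 6-month RFS is unchanged. State the reference for the remaining response conditions too. Keeping the pretreatment assessment is suggested: dexamethasone, given when clinically indicated (Section 5.1.6), and transient deficits (Section 13.3.2) may distort values just after surgery.
- (e) State whether the PR size rule is volumetric or a product of diameters.
- (f) Make no historical response comparison unless the comparator used a post-operative baseline.

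Costs: no added scan, but the evaluable subset may be small and is selected for incomplete resection. If 5, 10 or 15 of the 30 patients qualified (assumed sizes), zero responses would leave an upper exact 95% limit, 1 − 0.025^(1/n), of 52%, 31% or 22%, against 12% with all 30. A response first seen at Week +4 (Day 25 to 31) needs confirmation at Day 53 to 59 or later. MRI is then only as clinically indicated until Week +24, and other therapy may have begun. The reference scan also follows PDT.
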